Any potentially measurable lesion that has been previously treated with radiotherapy should be considered as a non-measurable lesion. However, if a lesion previously treated with radiotherapy has clearly progressed since the radiotherapy, it can be considered as a measurable lesion.

Each lesion that is measured at baseline must be measured by the same method (either same radiologic/nuclear method or by physical exam) throughout the study so that the comparison is consistent. Criteria required for determining partial or complete response should be present for at least 4 weeks.

Chest x-rays and ultrasound should not be used to measure tumor lesions.

Core Phase Treatment phase imaging assessments

Imaging assessments as described in Table 7-3 should be performed using the same imaging modality used at screening, irrespective of study treatment interruption or actual dosing. Imaging assessments for response evaluation will be performed every 12 weeks (+/- 7 days) during the Core Phase. The 12 week interval should be followed regardless of whether study treatment is temporarily withheld or unscheduled assessments are performed.

Additional imaging assessments may be performed at any time during the study at the investigator's discretion to support the efficacy evaluations for a subject, as necessary. Clinical suspicion of disease progression at any time requires a physical examination and imaging assessments to be performed promptly rather than waiting for the next scheduled imaging assessment.

Each lesion that is measured at screening must be measured by the same method (either same imaging method or by photography, including a metric ruler) and when possible, the same local radiologist/physician throughout the study so that the comparison is consistent. If an off-schedule imaging assessment is performed because progression is suspected, subsequent imaging assessments should be performed in accordance with the original imaging schedule.

Combined Positron Emission Tomography/Computed Tomography (PET/CT) may be used only if the CT is of similar diagnostic quality as a CT performed without PET, including the utilization of IV contrast media. At the discretion of the Investigators, FDG-PET scans may be performed to document progressive disease per RECIST v1.1 (Appendix 5).

Extension Phase

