10.5.1 Secondary efficacy objective(s)

10.5.1.1 Progression free survival

PFS is defined as the time from the date of first dose of study medication to the date of the first documented progression or death due to any cause occurring in the study. PFS will be assessed based on local investigator's assessment according to RECIST v1.1 (see Appendix 5 for further details).

PFS will be censored if no PFS event is observed before the cut-off date. The censoring date will be the date of last adequate tumor assessment before the cut-off date. If a PFS event is observed after two or more missing or non-adequate tumor assessments, then PFS will be censored at the last adequate tumor assessment. If a PFS event is observed after a single missing or non-adequate tumor assessment, the actual date of event will be used (see Appendix 5). It is not intended to censor patients for new anticancer therapy prior to documented disease progression in the primary analysis.

The Kaplan-Meier estimate of the PFS survival function will be estimated and displayed. The resulting median PFS time will be given for each cohort with 95% confidence intervals, as well as 25th and 75th percentiles will be reported.

10.5.1.2 Progression free survival 2

PFS2 is defined as time from the date of first dose of study medication to the date of first documented progression on next-line therapy or death from any cause.

The first documented progression on next-line treatment is based on investigator assessment of PD (i.e. as captured on the anti-neoplastic therapy after treatment discontinuation eCRF page);

it is not necessary to continue to collect tumor assessments data for subsequent anti-neoplastic therapies for the purpose of PFS2.

PFS2 will be summarized using the Kaplan-Meier method on the mFAS. The resulting median PFS will be given with 95% confidence intervals for each cohort.

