Situation F: New cancer therapy given: the handling of this situation must be specified in detail in the protocol. However, option (1), (ITT) is the recommended approach; events documented after the initiation of new cancer therapy will be considered for the primary analysis i.e. progressions and deaths documented after the initiation of new cancer therapy would be included as events. This will require continued follow-up for progression after the start of the new cancer therapy. In such cases, it is recommended that an additional sensitivity analysis be performed by censoring at last adequate assessment prior to initiation of new cancer therapy.

Option (2), i.e. censoring at last adequate assessment may be used as a sensitivity analysis. If a high censoring rate due to start of new cancer therapy is expected, a window of approximately 8 weeks performed after the start of new cancer therapy can be used to calculate the date of the event or censoring. This should be clearly specified in the analysis plan.

In some specific settings, local treatments (e.g. radiation/surgery) may not be considered as cancer therapies for assessment of event/censoring in PFS/TTP/DoR analysis. For example, palliative radiotherapy given in the trial for analgesic purposes or for lytic lesions at risk of fracture will not be considered as cancer therapy for the assessment of BOR and PFS analyses. The protocol should clearly state the local treatments which are not considered as antineoplastic therapies in the PFS/TTP/DoR analysis.

The protocol should state that tumor assessments will be performed every x weeks until radiological progression irrespective of initiation of new antineoplastic therapy. It is strongly recommended that a tumor assessment is performed before the patient is switched to a new cancer therapy.

Additional suggestions for sensitivity analyses

Other suggestions for additional sensitivity analyses may include analyses to check for potential bias in follow-up schedules for tumor assessments, e.g. by assigning the dates for censoring and events only at scheduled visit dates. The latter could be handled by replacing in Table 3-2 the "Date of last adequate assessment" by the "Date of previous scheduled assessment (from baseline)", with the following definition:

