2.7.1 Secondary endpoints

The mFAS will be used for the secondary efficacy analyses.

Progression free survival

Secondary endpoints include PFS, defined as the time from the date of start of treatment to the date of the first documented progression or death due to any cause. PFS will be based on local investigators review of tumor assessments and using RECIST 1.1 criteria (see Appendix 5 of the study protocol). If a patient has not progressed or died at the analysis cut-off date, PFS will be censored at the date of the last adequate tumor evaluation date before the cut-off date. PFS events documented after the initiation of new anti-neoplastic therapy (i.e. RECIST 1.1 documented disease progression or death) will be considered for the primary analysis provided tumor assessments continue after initiation of new cancer therapy. Discontinuation due to disease progression (collected on the 'End of treatment' and 'End of post treatment follow up' disposition pages) without supporting objective evidence satisfying progression criteria per RECIST 1.1 will not be considered disease progression for PFS derivation. Clinical deterioration will not be considered as a qualifying event for progression.

Overall response rate

ORR is defined as the proportion of patients with best overall response (BOR) of complete response (CR) or partial response (PR) according to RECIST 1.1 (see Appendix 5 of the study protocol). ORR will be calculated based using local investigators review of tumor assessment data in patients with measurable disease at baseline. Patients with only non-measurable disease at baseline will be part of the analysis and will be included in the numerator only if a complete response was observed. Tumor assessments performed before the start of any further antineoplastic therapy (i.e. any additional secondary antineoplastic therapy or surgery) will be considered in the assessment of BOR.

Clinical benefit rate (CBR)

CBR is defined as the proportion of patients with a best overall response of CR or PR, or an overall lesion response of stable disease (SD) lasting 24 weeks or longer or Non-CR/ Non-PD lasting 24 weeks or longer, according to RECIST 1.1 criteria. A patient will be considered to have SD for 24 weeks or longer if a SD response is recorded at 23 weeks or later from

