2.7.3 Handling of missing values/censoring/discontinuations

PFS

PFS will be censored at the date of the last adequate tumor assessment if no PFS event is observed prior to the analysis cut-off date.

PFS events documented after the initiation of new anti-neoplastic therapy (i.e. RECIST 1.1 documented disease progression or death) will be considered for the primary analysis provided tumor assessments continue after initiation of new cancer therapy.

The date of last adequate tumor assessment is the date of the last tumor assessment with overall lesion response of CR, PR or SD before an event or a censoring reason occurred. In this case the last tumor evaluation date at that assessment will be used. If no post-baseline assessments are available (before an event or a censoring reason occurred) then the date of randomization/start date of treatment will be used.

In particular, PFS will be censored at the last adequate tumor assessment if one of the following occurs: absence of event, the event occurred after two or more missing tumor assessments. The term “missing adequate tumor assessment” is defined as a tumor assessment (TA) not performed or tumor assessment with overall lesion response of “UNK”. The rule to determine number of missing TAs is based on the time interval between the date of last adequate tumor assessment and the date of an event. If the interval is greater than twice the protocol-specified interval between the TAs and 2 times the protocol-allowed time window around assessments, then the number of missing assessments will be 2 or more.

Refer to [Table 2-5](#) for censoring and event date options and outcomes for PFS.

Table 2-5 Outcome and event/censor dates for PFS analysis

Situation	Date	Outcome
No baseline assessment	Date of start of treatment	Censored
Progression or death at or before next scheduled Assessment	Date of progression (or death)	Progressed

Situation	Date	Outcome
Progression or death after exactly one missing assessment	Date of progression (or death)	Progressed
Progression or death after two or more missing assessments	Date of last adequate assessment prior to missed assessment	Censored
No progression (or death)	Date of last adequate assessment	Censored
Treatment discontinuation due to 'Disease progression' without documented progression, i.e. clinical progression based on investigator claim	Date of last adequate assessment	Censored

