New anticancer therapy given prior to protocol defined progression	Ignore the new anticancer therapy and follow situations above	As per above situations
Death before first PD assessment	Date of death	Progressed

ORR

Patients with unknown or missing best overall response (BOR) will be counted as failures. If there is no baseline tumor assessment, all post-baseline overall lesion responses are expected to be 'Unknown'. If no valid post-baseline tumor assessments are available, the best overall response must be "Unknown" unless progression is reported. For the computation of ORR, these patients will be included in the mFAS and will be counted as 'failures'.

PFS 2

For PFS2, refer to [Table 2-6](#) for censoring and event date options and outcomes.

Table 2-6 Outcome and event/censor dates for PFS2 analysis

Situation	Event/Censoring Date	Outcome
No baseline assessment	Date of start of treatment	Censored
Progression or death during the next-line therapy	Date of progression (or death)	Event
Death prior to initiation of next-line therapy	Date of death	Event
No progression (or death) during the next-line therapy and no second new anti-neoplastic therapy is initiated	Last contact date	Censored
No progression (or death) during the next-line anticancer therapy and a second new anti-neoplastic therapy is initiated	End date of the next-line therapy	Censored
No next-line therapy initiated with patient known to be alive	Last contact date	Censored

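### SAP text counts a death after new anticancer therapy as a PFS event only if tumor scans continue, contrary to SAP Table 2-5 and the protocol

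*SAP*

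**What the plan says.** The relevant text is in the main SAP (Amendment 4), to which the extension-phase SAP refers for all main analyses.

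- **SAP 2.7.1**, the PFS definition: events recorded after a new anti-neoplastic therapy, named as RECIST 1.1 progression or death, "will be considered for the primary analysis provided tumor assessments continue after initiation of new cancer therapy".
- **SAP 2.7.3** repeats the sentence, again naming death: "or death) will be considered for the primary analysis provided tumor assessments continue after initiation of new cancer therapy".
- **SAP Table 2-5**, to which 2.7.3 refers for event and censoring dates, has a row for new therapy before progression: "Ignore the new anticancer therapy and follow situations above". The rows above it make a death at or before the next scheduled assessment, or after exactly one missing assessment, an event on the date of death. After two or more missing assessments the patient is censored at the last adequate one. A last row, "Death before first PD assessment", is also an event on the date of death. No row asks whether scanning went on after the switch.
- **Protocol 10.5.1.1**: "It is not intended to censor patients for new anticancer therapy prior to documented disease progression in the primary analysis".
- **Protocol Appendix 5, section 3.2.10**, situation F, on the recommended option (1): "progressions and deaths documented after the initiation of new cancer therapy would be included as events".

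**The concern.** The condition makes sense for RECIST progression, which cannot be documented without scans. It makes no sense for death, which needs no scan. Because the SAP text names death, a programmer working from the narrative could leave out deaths that a programmer working from Table 2-5 would count.

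The patients concerned are those who deteriorate clinically, change therapy without meeting RECIST progression, have no further imaging and die soon afterwards. The SAP does not accept clinical progression as a PFS event, so death is the only event such a patient can contribute. Censoring these patients at their last scan is informative: they leave the risk set because they are doing badly. At stake are the PFS medians and the 6-, 12- and 18-month rates that the SAP reports by cohort, and the PFS subgroup summaries.

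**Working it through.** **1. Where the two rules part.** Scans: "Imaging assessments for response evaluation will be performed every 12 weeks (+/- 7 days) during the Core Phase". The SAP counts two or more assessments as missing "If the interval is greater than twice the protocol-specified interval between the TAs and 2 times the protocol-allowed time window around assessments". With a 12-week interval and a 1-week window, the limit is 2×12 + 2×1 = 26 weeks (182 days) from the last adequate assessment.

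| Death after a switch, no further scans | Table 2-5 and protocol | SAP text read literally |
|---|---|---|
| Within 26 weeks of last adequate scan | Event on date of death | Not counted; censored at last scan |
| Beyond 26 weeks | Censored at last scan | Censored at last scan |

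Example: last adequate scan at week 12, switch at week 16, no more scans, death at week 30. The gap is 30 − 12 = 18 weeks, with one scan missed, so the table gives an event at week 30 and the text gives censoring at week 12. With death at week 40 the gap is 28 weeks and both censor at week 12. I take the table's row on death before the first PD assessment as subject to the missing-assessment rule. A wider reading of that row would enlarge the gap between table and text.

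**2. Size.** The documents give no rate of switching without progression, so this is an illustration on assumed inputs:

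- exponential PFS with a true median of 4.5, 6 or 8 months (the sample-size section cites at least 6 months in an earlier population);
- a fraction f of patients fully affected, that is, they stop scanning at their last 12-weekly scan and die at a uniformly distributed time 1 to 26 weeks later;
- no other censoring, and 400,000 simulated patients per row.

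In a cohort of 112, f = 2% to 10% is 0.02×112 = 2.2 to 0.10×112 = 11.2 patients.

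| True median (months) | f | KM median, table → text | Rise (months) | 12-month PFS %, table → text | Rise (points) |
|---|---|---|---|---|---|
| 4.5 | 2% | 4.54 → 4.56 | 0.02 | 15.8 → 16.2 | 0.4 |
| 4.5 | 10% | 4.74 → 4.90 | 0.16 | 16.3 → 18.4 | 2.1 |
| 6 | 2% | 6.04 → 6.11 | 0.07 | 25.1 → 25.6 | 0.5 |
| 6 | 5% | 6.10 → 6.27 | 0.17 | 25.3 → 26.5 | 1.2 |
| 6 | 10% | 6.20 → 6.56 | 0.36 | 25.7 → 28.2 | 2.5 |
| 8 | 2% | 8.01 → 8.11 | 0.10 | 35.3 → 35.8 | 0.5 |
| 8 | 10% | 8.20 → 8.78 | 0.58 | 35.9 → 38.8 | 2.9 |

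Only the comparison within a row matters. The table column drifts up with f because the assumed deaths fall after the scan that precedes the patient's simulated PFS time.

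**3. Against sampling error.** The approximate standard error of the 12-month rate is √(p(1−p)/112):

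- p = 0.163: 3.5 points, against a shift of 2.1
- p = 0.257: 4.1 points, against 2.5
- p = 0.359: 4.5 points, against 2.9

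Every shift is within one standard error.

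**4. Direction.** The shift was upward in every row, but this does not hold at every time point. Take three patients: events at 2 and 3, censoring at 5. Then S(2) = 2/3 = 0.67. Recode the event at 3 as censored at 1: only two are at risk at time 2, so S(2) = 1/2 = 0.50, which is lower. From time 3 on, the curve is 0.50 instead of 0.33, which is higher.

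**5. Primary endpoint.** Protocol 10.4.3 and SAP 2.5.3 count death, progression or study discontinuation before 6 months as failure. The design figures reproduce: with p0 = 0.30 (protocol summary), P(X ≥ 44 of 112) = 0.0225, and power at 0.45 is 0.9055. Nothing in this point changes them.

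**The case against.** The strongest reply is that the literal rule is only implied. No sentence says that a death after a switch without scans is censored. Section 2.7.3 lists what leads to censoring at the last adequate assessment, namely no event, or an event after two or more missing assessments, and then sends the reader to Table 2-5. Appendix 5 also follows its statement that deaths after new therapy are events with a remark that this requires follow-up for progression to continue. The SAP condition may be a shortened form of that remark. The SAP's sixth PFS2 rule uses the same idea for progression alone. Finally, the protocol has scans continue every 12 weeks until progression whatever the reason for stopping treatment (4.1, 4.3, 7.1.5, 7.1.8) and strongly recommends one before a switch, so affected patients should be few.

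Much of this stands. The table's rule is probably the intended one, and the affected group should be small. But the condition names death, appears twice, and is not overridden anywhere: the cross-reference to Table 2-5 does not say that the table prevails over the text. SAP section 4, on changes to protocol-specified analyses, covers only COVID-19 and declares no departure. The duration-of-response paragraph adds doubt, since it describes the PFS rule as options F(1-3), a range that includes two options that do censor for new therapy.

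**Conclusion.** The inconsistency is real and should be corrected. Its likely effect is small: on the assumption that 2–10% of patients are affected, the median rises by roughly 0.02–0.6 months and 12-month PFS by roughly 0.4–2.9 points.

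Stronger conclusions that a reader might draw are not supported:

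- *That the plan definitely drops these deaths.* It contains two conflicting statements, and the table may well be the one that was programmed.
- *That PFS always moves up.* The net effect is usually upward, but the curve can be lower between the last scan and the date of death.
- *That the median could shift by more than a month.* A harsher simulation with 12-weekly scans (30% assumed to switch and stop scanning, median survival 6 months afterwards) moved the typical median from 6.9 to 8.3 months. But 8.3 months is the week-36 scan (252/30.4375 = 8.28), so the move is partly a jump between scan dates, and the 30% has no source in the documents.
- *That the primary endpoint is affected,* because the sentence speaks of the primary analysis. It sits in the PFS rules, and the 6-month proportion has its own failure rule. PFS itself is secondary and estimated by cohort without a test.

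**What to change.** In SAP 2.7.1 and 2.7.3, limit the continued-assessment condition to RECIST progression. State that a death after new therapy follows Table 2-5, subject only to the rule on two or more missing assessments, and that Table 2-5 governs where text and table differ. Suggested wording: progression documented after new anti-neoplastic therapy is counted when tumor assessments continue; death after new therapy is handled as in Table 2-5. Then check that the PFS program does the same.

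The cost is one sentence in two places and a program check. The sample size and the primary analysis do not change. PFS may come out slightly less favourable if the program had followed the text.

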3.2.10 Sensitivity analyses

This section outlines the possible event and censoring dates for progression, as well as addresses the issues of missing tumor assessments during the study. For instance, if one or more assessment visits are missed prior to the progression event, to what date should the progression event be assigned? And should progression event be ignored if it occurred after a long period of a patient being lost to follow-up? It is important that the protocol and RAP specify the primary analysis in detail with respect to the definition of event and censoring dates and also include a description of one or more sensitivity analyses to be performed.

Based on definitions outlined in Section 3.2.8, and using the draft FDA guideline on endpoints (Clinical Trial Endpoints for the Approval of Cancer Drugs and Biologics, April 2005) as a reference, the following analyses can be considered:

Table 3-2 Options for event dates used in PFS, TTP, duration of response

		Options for end-date (progression or censoring) ¹ (1) = default unless specified differently in the protocol or RAP	Outcome
Α	No baseline assessment	(1) Date of randomization/start of treatment ³	Censored
В	Progression at or before next scheduled assessment	 (1) Date of progression (2) Date of next scheduled assessment² 	Progressed Progressed
C1	Progression or death after exactly one missing assessment	 (1) Date of progression (or death) (2) Date of next scheduled assessment² 	Progressed Progressed
C2	Progression or death after two or more missing assessments	 (1) Date of last adequate assessment² (2) Date of next scheduled assessment² (3) Date of progression (or death) 	Censored Progressed Progressed
D	No progression	(1) Date of last adequate assessment	Censored
E	Treatment discontinuation due to 'Disease progression' without documented progression, i.e. clinical progression based on investigator claim	(1) Ignore clinical progression and follow situations above(2) Date of discontinuation (visit date at which clinical progression was determined)	As per above situations Progressed
F	New anticancer therapy given	 (1) Ignore the new anticancer therapy and follow situations above (ITT approach) (2) Date of last adequate assessment prior to new anticancer therapy (3) Date of secondary anti-cancer therapy (4) Date of secondary anti-cancer therapy 	As per above situations Censored Censored Event

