G	Deaths due to reason other than deterioration of 'Study indication'	(1) Date of last adequate assessment	Censored (only TTP and duration of response)

=Definitions can be found in Section 3.2.8

=After the last adequate tumor assessment. "Date of next scheduled assessment" is defined in Section 3.2.8.
=The rare exception to this is if the patient dies no later than the time of the second scheduled assessment as defined in the protocol in which case this is a PFS event at the date of death.

The primary analysis and the sensitivity analyses must be specified in the protocol. Clearly define if and why options (1) are not used for situations C, E and (if applicable) F.

Situations C (C1 and C2): Progression or death after one or more missing assessments: The primary analysis is usually using options (1) for situations C1 and C2, i.e.

- (C1) taking the actual progression or death date, in the case of only one missing assessment.
- (C2) censoring at the date of the last adequate assessment, in the case of two or more consecutive missing assessments.

In the case of two or missing assessments (situation C2), option (3) may be considered jointly with option (1) in situation C1 as sensitivity analysis. A variant of this sensitivity analysis consists of backdating the date of event to the next scheduled assessment as proposed with option (2) in situations C1 and C2.

Amended Protocol Version 06 (Clean)

Situation E: Treatment discontinuation due to 'Disease progression' without documented progression: By default, option (1) is used for situation E as patients without documented PD should be followed for progression after discontinuation of treatment. However, option (2) may be used as sensitivity analysis. If progression is claimed based on clinical deterioration instead of tumor assessment by e.g. CT-scan, option (2) may be used for indications with high early progression rate or difficulties to assess the tumor due to clinical deterioration.

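### SAP Table 2-5 censors PFS at a clinical-progression stop, against the protocol default and the SAP's own text; the duration-of-response options and the OS analysis set also need reconciling

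*SAP*

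**What the plan says.** **PFS, protocol.** Appendix 5, Table 3-2, row E deals with treatment stopped for disease progression that was not documented. Its default, option (1), is "Ignore clinical progression and follow situations above". Text below the table tells the authors to "Clearly define if and why options (1) are not used for situations C, E and (if applicable) F". Protocol 10.5.1.1 sets no different rule for this situation.

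**PFS, SAP Amendment 4.** Table 2-5 (SAP 2.7.3) repeats the situation as "Treatment discontinuation due to 'Disease progression' without documented progression, i.e. clinical progression based on investigator claim", but dates it at the last adequate assessment with outcome *Censored*. Other SAP text reads differently:

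- SAP 2.7.1 defines PFS to include death from any cause. It says that a stop for disease progression "without supporting objective evidence satisfying progression criteria per RECIST 1.1 will not be considered disease progression for PFS derivation". That denies the claim event status and does not make it a reason to censor.
- The 2.7.3 prose names two triggers for censoring at the last adequate assessment: "absence of event, the event occurred after two or more missing tumor assessments".
- The duration-of-response (DOR) paragraph in 2.7.1 says the PFS censoring rule uses E(1).
- The last row of Table 2-5, "Death before first PD assessment", has the outcome *Progressed*, as do the rows for progression or death after no more than one missing assessment.

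**DOR.** The same paragraph cites options F(1-3) for new anticancer therapy. Table 2-5 uses F(1) for PFS: "Ignore the new anticancer therapy and follow situations above".

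**OS.** Protocol 10.5.1.6 bases OS on the FAS. SAP 2.7.1 and 2.7.2 use the mFAS. SAP Section 4, which is the place for changes to protocol-specified analyses, covers COVID-19 only.

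**The concern.** A programmer working from Table 2-5 alone would censor a patient at the scan before a clinical-progression stop, even if RECIST progression or death followed soon after. Patients stopped for clinical deterioration are at high risk of an event, so such censoring is informative and pushes PFS upward. It would reach the medians, the 6-, 12- and 18-month rates (SAP 2.7.2) and the PFS subgroup summaries (SAP 2.2.1). A programmer working from the prose would count those events, so the same data could give two PFS datasets.

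The later events are observable. Protocol 7.1.5 and 7.1.8 keep Core Phase scans going every 12 weeks unless progression was documented, and 7.1.9 collects survival regardless of the reason for stopping.

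The DOR citation cannot be programmed as written. Option F(1) ignores new therapy, F(2) censors at the last adequate assessment before it, and F(3) censors at its start date.

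For OS, the protocol and the SAP name different denominators, and a reader of the report would not learn that the set had changed.

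**Working it through.** **1. The primary endpoint is separate.** With a null rate of 0.30 (protocol summary) and success at 44 or more of 112, the exact one-sided alpha is 0.0225 and the power at 0.45 is 0.9055. This agrees with the stated 2.5% and at least 90%. The endpoint is a count with its own failure rule (SAP 2.5.3) and does not use Table 2-5.

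**2. The window in which the two rules differ.** SAP 2.7.3 treats two or more assessments as missing when the gap from the last adequate scan is "greater than twice the protocol-specified interval between the TAs and 2 times the protocol-allowed time window around assessments". Protocol 7.2.1.1 gives 12 weeks ± 1 week, so the limit is 2×12 + 2×1 = 26 weeks. Beyond 26 weeks both rules censor at the last adequate scan. With no later event both rules censor at the same date. They differ only for a progression or death within 26 weeks.

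**3. Two worked patients.** Both have stable disease at week 12 and stop for clinical progression at week 16.

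| Later event | E(1) and SAP prose | Clinical-progression row, literal |
|---|---|---|
| RECIST progression at week 24 | Event, week 24 | Censored, week 12 |
| Death at week 20, no documented progression | Event, week 20 | Censored, week 12 |

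The second patient has no documented progression, so the softer reading of the row does not remove the clash with the *Progressed* rows.

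**4. Size per dropped event.** Assumptions: n=112, 6-month PFS near 45% or 50% (both figures appear in protocol 10.8), progression dated at the week-12 and week-24 scans, and no other censoring.

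Near 45%: 37 events at week 12 leave 75, and 25 events at week 24 leave 50. The rate is 50/112 = 44.6%.
- One week-12 event dropped (censored at start): (75/111)(50/75) = 50/111 = 45.0%, **+0.4**.
- One week-24 event dropped (censored at week 12): (75/112)(50/74) = 45.2%, **+0.6**.

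Near 50%: 33 events leave 79, and 23 leave 56. The rate is 56/112 = 50.0%.
- Week-12 event dropped: 56/111 = 50.45%, **+0.45**.
- Week-24 event dropped: (79/112)(56/78) = 50.64%, **+0.64**.

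Three dropped events give from 50/109 = 45.9% (**+1.2**) in the 45% case to (79/112)(56/76) = 52.0% (**+2.0**) in the 50% case. If no event is dropped, the shift is 0.

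For scale, the 95% half-width at 45% is 1.96 × √(0.45×0.55/112) = 9.2 points.

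**5. OS set.** Protocol 7.1.5.1 replaces patients without central confirmation of the mutation, so the FAS exceeds the mFAS whenever confirmation fails in a treated patient. Enrolment was 380. If all were treated and each cohort's mFAS holds at least 112 (both assumptions), at most 380 − 3×112 = 44 patients (11.6%) are left out. The actual figure is not given.

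**The case against.** The strongest reply is that the row means what its label says. A patient with later RECIST progression has documented progression and belongs in the progression rows; a patient with no later event is censored at the same date as in the no-progression row. The PFS definition, the two-trigger prose and the E(1) citation all support that reading. It is a fair reading, and for later RECIST progression it removes the harm. It does not settle a death without documented progression, which still matches rows with opposite outcomes.

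Table 3-2 also lets the analysis plan choose another option, and the instruction to explain a departure is generic guideline text. That stands: the fault is an unexplained inconsistency, not a forbidden choice.

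Such stops should be uncommon. Treatment runs to radiologically documented progression (6.1.5), suspected progression calls for prompt imaging (7.2.1.1), and an end-of-treatment scan is due if the last is older than 30 days (7.1.5). This limits the likely count but does not give it.

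Three stronger inferences are tempting but not supported:

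- *The new-therapy row adds a second conflict because the situations above it include the disputed row.* The protocol table has the same layout, and SAP 2.7.3 says directly that events after new therapy count.
- *Scans stop after a clinical-progression stop.* Protocol 4.3 is loosely worded, but 7.1.5 and 7.1.8 make the exception documented progression.
- *The row also governs extension-phase results.* The extension SAP refers main analyses back to Amendment 4 but plans no PFS analysis itself.

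On OS, protocol 10.1.1 names the mFAS as the primary efficacy set, so the protocol is in tension with itself. The OS sentence is the more specific one, and the SAP does not declare its choice.

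**Conclusion.** The inconsistency is real and of low to moderate importance. One row of Table 2-5 disagrees with the protocol default and with three statements in the SAP, and deaths after a clinical-progression stop remain ambiguous on any reading. Applied literally, it biases secondary PFS upward by about 0.4 to 0.6 points in the 6-month rate per dropped event at n=112, under the assumptions above. The number of affected patients is unknown and may be zero.

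A reader might infer that the SAP deliberately adopted a more favourable PFS rule, or that a material share of events will be lost. The documents support neither: the surrounding text points to E(1), and no rate of such stops is given. PFS is a secondary endpoint with no hypothesis test, and the primary endpoint and sample size are untouched.

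The F(1-3) citation is an error that needs correcting. The OS change is an undeclared mismatch affecting between 0 and about 44 patients under the stated assumptions. The documents do not show which way it would move OS.

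**What to change.** 1. In SAP Table 2-5, change the clinical-progression row to "Ignore clinical progression and follow situations above", and replace *Censored* with the outcome that protocol row E(1) carries, so that the other rows decide.
2. In the DOR rule of SAP 2.7.1, replace F(1-3) with F(1), to match PFS.
3. Analyse OS on the FAS as in protocol 10.5.1.6, with the mFAS as supportive; or record the change and its reason in SAP Section 4.

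The cost is SAP wording and programming, with no new data. PFS may come out slightly less favourable if any affected patients exist.
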